13.4.5 Analyses of Exploratory Endpoint(s)/Outcome(s)

Nasal fluid IL-33 and tryptase levels are expected to increase during aspirin-induced reactions and those increases will be compared between patients on ifetroban vs. placebo to determine if ifetroban treatment blunts the aspirin-induced increases. The IL-33 and tryptase levels will also be correlated to clinical symptoms (TNSS and fall in FEV1). We will measure the incremental increase in platelet or mast cell-derived chemokines in the nasal fluid during aspirin-induced reactions for patients on ifetroban vs. placebo and determine if those increases are blunted by ifetroban or correlate with the increase in nasal eicosanoids during reaction.

13.4.6 Descriptive Analyses

Summary of descriptive statistics for baseline and demographic characteristics will be provided for all enrolled participants. Demographic data will include age, race, sex, body weight, and height; these data will be presented in the following manner: Age, body weight, and height will be averaged per treatment group. Race and sex will be summarized as the number and percent of subjects in each category. Baseline control and severity of asthma will be provided as tabular summaries of average baseline ACQ score, average baseline FEV₁ as percent of predicted, and average baseline daily corticosteroid use.

The percent of participants who complete the study, losses to follow-up, time to lost to follow-up, and reasons for discontinuation (e.g., adverse events) will be presented.

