suspected AERD will be enrolled in this study with the anticipation that there will be a dropout rate of 10-20%. All subjects will have a clinical history consistent with AERD (asthma, nasal polyposis, and a history of a suspected reaction to a nonselective COX inhibitor). All subjects will be on standard therapy for persistent asthma, which may include some combination of inhaled glucocorticoids, oral glucocorticoids, long- and short-acting β -agonists, and CysLT₁R antagonists. We will exclude individuals being treated with omalizumab (monoclonal anti-IgE) or mepolizumab (monoclonal anti-IL-5), as the effects of these medications on the aspirin-induced reactions in AERD are not known. Detailed Inclusion and Exclusion criteria are listed in Section 4.2 and 4.3. We have found that all of the subjects who are currently enrolled in our trial of prasugrel and meet these strict inclusion criteria exhibited respiratory reactions to aspirin, confirming their diagnosis of AERD. The Study Schema overview is shown in **Figure 3**.

At a Screening Visit for patients with AERD, the study will be explained, and the participant will sign informed consent before undergoing any procedures. A physical exam, baseline ECG, spirometry and lab work (CBC, urine pregnancy) will be performed. Assessments of asthma control (ACQ score, which evaluates asthma control over the preceding 1 week), and nasal symptoms (SNOT-22 score, which assesses symptoms over the preceding 2 weeks) will also be obtained.

There will be a 2-week Run-In after the Screening Visit during which subjects will begin taking montelukast 10mg daily (if not already on montelukast as part of their regular asthma care) and will stop taking zileuton (if they are on

zileuton as part of their regular asthma care). A telephone encounter (**Phone Call 1**) 1 week later will ensure safety and confirm stable asthma.

After the 2-week Run-In Period on montelukast, subjects will come into the ARC for **Visit 1**. Interval history, physical exam, ACQ, SNOT-22, pre-challenge TNSS and spirometry will be recorded, along with FeNO. Blood will be drawn for CBC/differential, and cellular profiling and activation assays. A urine sample will be collected for pregnancy and eicosanoid metabolites. Nasal lavage for cytokine and eicosanoid measurements and a nasal epithelial scraping sample for RNA extraction will be taken. Subjects will be randomized to receive ifetroban (200 mg dose per day), or placebo for 4 weeks.

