Subjects will take ifetroban or placebo daily for 4 weeks and will continue taking daily montelukast. There will be a telephone encounter (**Phone Call 2**) 1 week into this Treatment Period to ensure safety and confirm that chronic asthma symptoms have not worsened.

After the 4-week treatment period, subjects will come into the ARC for **Visit 2**. Before aspirin is given, interval history, physical exam, ACQ, SNOT-22, TNSS, and spirometry will be recorded, along with FeNO, and a urine sample will be collected for pregnancy and eicosanoid metabolites. Nasal lavage and a nasal epithelial scraping sample will also be taken (prior to the TNSS questionnaire to ensure that the procedures do not affect the symptom assessment), along with a blood draw for CBC/differential and cellular assays. After waiting at least 15 minutes following the nasal lavage and scraping so that any nasal irritation has subsided, subjects will then undergo an oral aspirin desensitization procedure. They will receive an initial 40.5 mg dose of aspirin, and then every 90 minutes will be given increasing doses of 81, 162, and 325 mg aspirin. Vital signs are obtained every 90 minutes during the aspirin challenge/desensitization. If at any point the subject develops symptoms of a reaction, we will examine them and record the time of onset of reaction. The dose of reaction that induces an increase in TNSS of 2 or more points will be recorded as the provocative dose.

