4.3. Exclusion Criteria

Individuals who meet any of these criteria are not eligible for enrollment as study participants:

1. Inability or unwillingness of a participant to give written informed consent or comply with study protocol
2. Hypersensitivity to montelukast
3. Current use of zileuton (which blunts the peak levels of urinary LTE₄ during reactions)
4. Any history of bleeding diathesis or current use of anticoagulant/antiplatelet drugs
5. Any history of gastrointestinal bleeding
6. Current use of oral beta blockers, though ophthalmic formulations are acceptable

7. The use of an additional non-steroidal anti-inflammatory drugs (NSAIDs), except the aspirin dosing as detailed for the study
8. Use of any biologic therapy within the prior 4 months (120 days) of Visit 1.
9. History of cardiac rhythm disturbances.
10. Heart rate of <50 bpm at Screening Visit, or evidence of any type of heart block on ECG at Screening Visit.
11. Pregnant, nursing, or planning to become pregnant.
12. Past or current medical problems or findings from physical examination or laboratory testing that are not listed above, which, in the opinion of the investigator, may pose additional risks from participation in the study, may interfere with the participant's ability to comply with study requirements or that may impact the quality or interpretation of the data obtained from the study.
13. Evidence of liver failure (AST or ALT levels >3x normal at Screening)
14. Evidence of kidney failure (creatinine levels >1.5mg/dl in women and >1.7mg/dl in men)

5. Known and Potential Risks and Benefits to Participants

5.1. Risks of Investigational Product or Intervention as cited in Investigator Brochure or Package Insert

Risks of Ifetroban:

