The pharmacodynamics of ifetroban were studied in single- and repeat-dose safety studies and in an ifetroban and aspirin interaction study in healthy volunteers. In the single-dose study, bleeding time was prolonged (2x baseline) in subjects receiving doses of ifetroban greater than 10 mg. Platelet aggregation induced by the TP receptor agonist U46619 was inhibited by all doses of ifetroban including 10 mg. This effect lasted for up to six days for the highest dose (1000 mg). Ifetroban also blocked arachidonic acid-induced platelet aggregation and partially inhibited collagen-induced aggregation. While epinephrine-induced primary aggregation was not affected by ifetroban, the secondary aggregation (degranulation) appeared to be inhibited. There was no drug effect on ADP-induced aggregation. Ifetroban alone or in combination with aspirin inhibited U46619-induced platelet aggregation. Treatment with aspirin alone did not prevent U46619-induced aggregation. Bleeding time was prolonged after all doses following the single dose and at steady state, although no dose-dependent increase in bleeding time was observed. No indication of accumulation effect was seen after nine days of dosing. No significant effect on urinary excretion of TXA₂ and prostacyclin metabolites was observed. In the aspirin interaction study, urinary excretion of both 2,3-dinor-TXB₂ and 2,3-dinor-6-keto-PGF_{1α} was decreased after administration of 325 mg of aspirin alone and 325 mg of aspirin + 250 mg ifetroban. Administration of ifetroban alone had no effect on urinary excretion of either 2,3-dinor-TXB₂ or 2,3-dinor-6-keto-PGF_{1α}. Thus, TP receptor blockade has no effect on the synthesis of vasoprotective PGI₂. *Of specific importance to our proposed trial, no significant safety concerns emerged in the studies of ifetroban with aspirin.*

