Ifetroban was the subject of 24 controlled and uncontrolled human pharmacology and pharmacokinetic studies. It was also the subject of eight placebo-controlled clinical trials for various cardiovascular indications which are summarized in **Table 2**. The incidence rate of adverse events was generally comparable between the ifetroban-treated subjects and the placebo-treated subjects. Bradycardia was reported more often in the ifetroban group (N=32; 3.3%) than with placebo (N=7; 1.2%). Gastrointestinal events tended to occur more often in the ifetroban subjects than in the placebo subjects, although incidence rates were too small to suggest a trend or pattern. The most frequently reported adverse events (N; % ifetroban vs. N; % placebo) were headache (N=80; 8.4 vs. N=47; 7.7), musculoskeletal pain (N=48; 5.0 vs. N=19; 3.1), angina pectoris (N=33; 3.5 vs. N=22; 3.6), bradycardia (N=32; 3.3 vs. N=7; 1.2), myocardial infarction (N=28; 2.9 vs. N=18; 3.0), nausea/vomiting (N=25; 2.6 vs. N=10; 1.6), dyspepsia (N=24; 2.5 vs. N=9; 1.5), upper respiratory infection (N=24; 2.5 vs. N=9; 1.5), hematoma (N=23; 2.4 vs. N=8; 1.3), coronary artery bypass (N=22; 2.3 vs. N=10; 1.6), coronary angioplasty (N=21; 2.2 vs. N=10; 1.6), abdominal pain (N=20; 2.1 vs. N=10; 1.6), and anxiety/nervousness (N=19; 2.0 vs. N=9; 1.5). All remaining events occurred at a rate less than 2.0% in both treatment groups except for dizziness which occurred in 2.1% (N=13) of placebo-treated subjects (ifetroban: N=13; 1.9%).

Table 2. Number of subjects exposed to ifetroban in clinical studies.

		Subject Exposure	
		Ifetroban	Placebo
Clinical Pharmacology/Pharmacokinetics			
	Human Pharmacology	189	49
	Pharmacokinetic	154	0
Clinical Trials			
	Silent Ischemia (CV124-008)	58	55
	Stable angina (CV124-009)	105	52
	Unstable angina (CV124-011)	315	166
	PTCA (CV124-012)	90	35
	PVD (CV124-014)	137	44
	Post MI (CV124-015)	149	149
	Forearm blood flow in HF (CV124-018)	20	23
	Venous ulcers (CV139-001)	82	83
	Total Subjects	1299	656

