12.8.3 DSMB Review

12.8.3.1 Planned DSMB Reviews

The Data and Safety Monitoring Board (DSMB) shall review safety data at least yearly during planned DSMB Data Review Meetings. Data for the planned safety reviews will include, at a minimum, a listing of all reported AEs and SAEs.

The DSMB will be informed of an Expedited Safety Report in a timely manner. DSMB notification will occur as soon as site personnel are aware of the event but no later than 72 hours, which aligns with the requirements set forth by institutional guidelines.

12.8.3.2 *Ad hoc* DSMB Reviews

In addition to the pre-scheduled data reviews and planned safety monitoring, the DSMB may be called upon for *ad hoc* reviews. The DSMB will review any event that potentially impacts safety at the request of the protocol chair or DAIT/NIAID. In addition, the following events will trigger an *ad hoc* comprehensive DSMB Safety Review:

- Any death that occurs in the study, which is possibly or definitely related to study treatment regimen.
- The occurrence of a Grade 3 or higher related and unexpected SAE in 3 or more of the study participants who have received a study treatment.

After review of the data, the DSMB will make recommendations regarding study conduct and/or continuation.

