15.3. Privacy and Confidentiality

A participant's privacy and confidentiality will be respected throughout the study. Each participant will be assigned a unique identification number and these numbers rather than names will be used to collect, store, and report participant information. Site personnel will not transmit documents containing personal health identifiers (PHI) to the study sponsor or their representatives.

16. Publication Policy

The ICJME (International Committee of Medical Journal Editors) policy on the publication of study results will apply to this trial.

17. Appendix 1. Schedule of Events

Schedule of Events	Study Phase	Screen	Run-In	Treatment Period			Follow-up	
	Week	0	1	2	3	6	7	8
	Visit	V0	Phone Call 1	V1	Phone Call 2	V2	Phone Call 3	Phone Call 4
Procedures/Assessments								
	Informed Consent, Verify eligibility	+						
	Randomization (ifetroban/placebo)			+				
	Physical Exam and vital signs	+		+		++		
	Baseline symptoms (ACQ, SNOT-22)	+		+		+		
	Spirometry	+		+		++		
	Start montelukast	+						
Urine for:	Pregnancy test	+		+		+		
	Eicosanoids			+		++		
Blood for:	CBC/differential	+		+		+		
	Creatinine, LFTs	+						
	Platelet/WBC studies			+		++		
	Nasal washings/scrape samples			+		++		
	FeNO			+		+		
	Aspirin desensitization					+		
	Acute sinonasal symptoms (TNSS)					++		
	Initiation of aspirin therapy					+		
	Adverse event assessment		+	+	+	+	+	+

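### Heart rate and CBC are scheduled before and on drug in both arms, but no planned analysis compares any safety measure by arm

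*Combined protocol and SAP*

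**What the plan says.** **Known effects of the drug.** Section 5.1 (Risks of Ifetroban) states: "Bradycardia was reported more often in the ifetroban group (N=32; 3.3%) than with placebo (N=7; 1.2"%). It also states: "Bleeding time was prolonged after all doses following the single dose and at steady state". The same section gives hematoma at 2.4% against 1.3%. Section 4.3 excludes "Heart rate of <50 bpm at Screening Visit, or evidence of any type of heart block on ECG at Screening Visit".

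**Measurements taken.** The Schedule of Events (Appendix 1) has a row "Physical Exam and vital signs" marked at Screening, Visit 1 and Visit 2, and a CBC row marked at the same visits. For Visit 1, section 3.1 says "Blood will be drawn for CBC/differential, and cellular profiling and activation assays". It also places a CBC before aspirin at Visit 2 and another one hour after reaction onset. During the challenge, "Vital signs are obtained every 90 minutes during the aspirin challenge/desensitization". The text places the ECG at Screening only, so vital signs are the only scheduled source of heart rate on drug.

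**Analyses planned.** Sections 13.4.2, 13.4.4 and 13.4.5 set out comparisons of PD₂, FEV₁, LTE₄, tryptase, ACQ, SNOT-22, FeNO, IL-33 and chemokines. Section 13.4.1 (analysis populations) is marked N/A. Section 13.4.6 covers baseline characteristics and disposition: "The percent of participants who complete the study, losses to follow-up, time to lost to follow-up, and reasons for discontinuation (e.g., adverse events) will be" … The outcome lists in 3.3 and 3.4 contain no heart rate, hemoglobin, platelet count or adverse-event comparison.

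**Safety review.** Section 12.8.3.1 says: "Data for the planned safety reviews will include, at a minimum, a listing of all reported AEs and SAEs". Section 12.8.2.1 gives the Independent Safety Monitor (ISM) the same minimum.

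**The concern.** The trial randomises patients to a drug with a documented heart-rate signal and a documented effect on bleeding time. It schedules a reading relevant to each before and during treatment, and then plans no use of the randomised contrast for either. The final report would owe the reader efficacy and mechanistic comparisons but no between-arm safety estimate of any kind.

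At this sample size a listing of events carries very little information, and a count of zero is easily over-read. Section 1.4 already cites a 16-subject AERD study as showing no adverse effects. Even if all 16 took ifetroban, the chance of seeing no bradycardia at a true rate of 3.3% is 0.967^16 = 58%.

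**Working it through.** **The plan's own figure first.** Section 13.4.2 states 83% power for PD₂ with 20 per arm, 60 (SD 42) against 180 (SD 170), two-sided 0.05.
- SE = √((42² + 170²)/20) = √1533.2 = 39.16; noncentrality = 120/39.16 = 3.06; Welch df = 21.3.
- Power = 83.2%. The stated figure reproduces and is not in dispute. The plan states no safety figure to check.

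**The documented signals.** The clinical-trial rows of Table 2 (section 5.1) sum to 956 on ifetroban and 607 on placebo.
- Bradycardia: 32/956 = 3.3% and 7/607 = 1.2%; Fisher p = 0.007.
- Hematoma: 23/956 = 2.4% and 8/607 = 1.3%; Fisher p = 0.14. This difference is not clear on its own; the bleeding-time finding is the firmer evidence.

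**What event counts can show here.** Assume the 3.3% and 1.2% rates carry over. Sizes are 20 per arm (completers) and 25 per arm (50 recruited, 1:1).

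| | n = 20 per arm | n = 25 per arm |
|---|---|---|
| Expected ifetroban cases, n × 0.033 | 0.66 | 0.83 |
| Chance of none on ifetroban, 0.967^n | 51% | 43% |
| Expected placebo cases, n × 0.012 | 0.24 | 0.30 |
| Exact Fisher power | below 0.1% | below 0.1% |

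By the normal approximation, 80% power for 3.3% against 1.2% needs about 782 per arm.

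**What the heart-rate readings can show.** The 95% CI half-width for a difference in mean change is t(0.975, 2n−2) × SD × √(2/n). With n = 20 this is 2.024 × 0.3162 × SD = 0.64 SD. The documents give no SD of change, so a range is assumed.

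| Assumed SD of change (bpm) | 6 | 8 | 10 | 12 |
|---|---|---|---|---|
| 95% CI half-width, n = 20 per arm (bpm) | 3.8 | 5.1 | 6.4 | 7.7 |
| Difference with 80% power, 0.91 SD (bpm) | 5.5 | 7.3 | 9.1 | 10.9 |

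With 25 per arm the half-width is 0.57 SD, or 3.4 to 6.8 bpm over the same range. These figures are for unadjusted change.

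**Which reading to use.** Visit 2 readings during the challenge are mixed with the effects of aspirin and albuterol, so the pre-aspirin value is the clean one. Section 12.2.1 defines symptomatic hypotension against that morning's baseline, which implies that a pre-aspirin set of vital signs is taken.

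**The case against.** A reader might infer that a drug effect on heart rate or bleeding would go unreported altogether. The documents do not support that. Events of grade 2 or higher go on the CRF (12.3.1), and abnormal results can count as adverse events (12.3.1, 12.4.2). The Medical Monitor gets monthly reports (12.8.1), the ISM and DSMB review at least yearly (12.8.2.1, 12.8.3.1), and all adverse events go into the Annual DSMB Report (12.5.2.1). Section 12.5.2.2 names an aggregate comparison with a control group as evidence for expedited reporting, though no section schedules one. The gap is confined to between-arm shifts and changes below grade 2.

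A reader might also infer that the trial would declare ifetroban safe on zero or one event. No section plans a safety conclusion, and even at 3.3% two or more cases have a 14% chance with 20 patients and 20% with 25.

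Further objections stand in part:
- The 3.3% comes from cardiovascular trials. This trial excludes low heart rate, heart block, rhythm-disturbance history and oral beta blockers, so the rate is an assumption, and a lower one would make counts even less informative.
- The continuous comparison is no cure. If 3.3% against 1.2% reflected a pure normal shift, that shift is about 0.42 SD of heart rate. Power with 20 per arm is then about 25% if the SD of change equals the heart-rate SD, and 58% if it is 0.6 of it (both ratios assumed). An effect confined to a few susceptible patients would show even less in a mean.
- CBC reflects bleeding only indirectly. The documented effects are on bleeding time and platelet aggregation, and platelet activation is already compared by arm as a mechanistic outcome (3.3).
- After Screening, heart rate is inferred from vital signs. The source-data list does not name vital signs and keeps the CBC as a printed copy, so some data entry may be needed.
- The early-withdrawal visit (11.4) lists a CBC but no vital signs, so a Visit 2 heart-rate analysis cannot cover every dosed subject.

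Section 13.5 being N/A adds little, since it concerns interim analyses only.

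**Conclusion.** The omission is real and limited. Followed as written, the plan yields no randomised estimate of any safety measure, although vital signs and CBC are scheduled before and on drug in both arms and the protocol itself names bradycardia and prolonged bleeding time as ifetroban effects. Event listings would carry individual cases of grade 2 or higher but are close to uninformative about a difference: 0.66 expected bradycardia cases among 20 completers if the 3.3% rate transfers.

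The heart-rate comparison would say more, with a half-width of about 3.8 to 7.7 bpm under the assumed SDs, but could still miss a modest effect. It should not be presented as the only informative evidence or as proof of safety. The conclusion rests on heart rate being part of vital signs and on a pre-aspirin reading being kept at Visit 2. The change is worth making because it adds an estimate the trial would otherwise lack, at little cost.

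**What to change.** Add a final safety analysis to section 13 (Statistical Considerations):

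1. Tabulate adverse events and SAEs by arm for all subjects who took at least one dose.
2. For dosed subjects with a pre-aspirin Visit 2 value, estimate the arm difference in heart rate with a 95% CI, adjusted for the Visit 1 value, and state the number missing per arm.
3. Do the same for hemoglobin and platelet count, labelled as supportive and indirect measures of bleeding.

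Present all of these as estimates, not hypothesis tests, and say that a modest effect could be missed at this sample size.

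The cost is SAP wording, a little extra analysis, and entry of the Visit 1 and pre-aspirin Visit 2 vital signs and CBC values into the study database if they are not already captured there. No new visits or samples are needed, and no clinical threshold or management rule changes.

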13.5 Interim Analyses

N/A

13.5.1 Interim Analysis of Efficacy Data**13.5.2 Interim Analysis of Safety Data****13.5.3 Futility Analysis****13.6 Statistical Hypotheses**

See sections 13.4.2 through 13.4.5 above for detailed comparisons.

13.7 Sample Size Considerations

Assuming that there will be a dropout rate of 10-20%, we will seek to recruit 50 individuals with suspected AERD from our new referrals to meet a target sample size of 40 to complete the study, with 20 in each treatment arm. We will enroll additional subjects if we have an unusually high dropout rate. As detailed in section 13.4.2, with this sample size of 20 patients per treatment arm, we will have 83% power to detect a 3-fold shift in PD₂ (or an average an increase in PD₂ to 180 for patients on ifetroban, with a standard deviation of 170), at a 0.05 level of significance.

13. Identification and Access to Source Data**13.1. Source Data**

The Principal Investigator will keep accurate records to ensure that the conduct of the study is fully documented. Data derived from source documents will be transferred to protocol-specific CRFs. Hard copy results of the following clinical evaluations and clinical laboratory evaluations will be maintained in the participant's protocol-specific binder, housed at the Asthma Research Center:

- Patient medical histories, concomitant medications, adverse event forms (results written onto CRF)
- CBC/differential (printed copy)
- PFTs (printed copy)
- FeNO (results written onto CRF by coordinator/investigator)
- Pregnancy test (results written onto CRF by coordinator/investigator)
- Physical exam (results written onto CRF by coordinator/investigator)
- Patient questionnaires (results written onto CRF by patient)
- Details of which biologic specimens collected at each visit (written onto CRF by coordinator/investigator)

The applicable clinical study data will be transferred to a password-secured REDCap database on a dedicated server.

Data derived from research laboratory evaluations (flow cytometry, eicosanoid and cytokine levels, cellular assays) will be stored as a hard copy (as applicable) within laboratory notebooks, or within the appropriate assay-specific software program as required for each type of analysis.

